## 1. ABBREVIATIONS

ACEi	Angiotensin-Converting Enzyme Inhibitor
ADA	Anti-Drug Antibodies
AE	Adverse Event
ARB	Angiotensin Receptor Blocker
AUC	Area Under the Curve
BPI	Brief Pain Inventory
CI	Confidence Interval
CKD	Chronic Kidney Disease
C max	Maximum Observed Plasma Drug Concentration
CRF	Case Report Form
CSR	Clinical Study Report
CV	Coefficient of Variation
DBL	Database Lock
ECG	Electrocardiography
eGFR	Estimated Glomerular Filtration Rate
ERT	Enzyme Replacement Therapy
FCE	Fabry Clinical Events
FD	Fabry Disease
Gb3	Globotriaosylceramide
GMR	Geometric Mean Ratio
HBsAg	Hepatitis B Surface Antigen
HCV	Hepatitis C Virus
HIV	Human Immunodeficiency Virus
IRR	Infusion Related Reaction
IV	Intravenous
KM	Kaplan-Meier
Lyso-Gb3	Globotriaosylsphingosine
MedDRA	Medical Dictionary for Regulatory Activities
MRI	Magnetic Resonance Imaging
MSSI	Mainz Severity Score Index
NSR	Normal Sinus Rhythm
PK	Pharmacokinetics
PrT	Prothrombin Time
PT	Preferred Term
PTT	Partial Thromboplastin Time
QoL	Quality of Life
SAE	Serious Adverse Event

SAP	Statistical Analysis Plan
SD	Standard Deviation
SOC	System Organ Class
SE	Standard Error
T 1/2	Terminal Elimination Half-life
TEAE	Treatment Emergent Adverse Event
T max	Time to Maximum Observed Plasma Drug Concentration
UPCR	Urine Protein to Creatinine Ratio
WHO	World Health Organization

## 2. INTRODUCTION

The statistical analysis plan (SAP) contains the analysis information in detail on the definition of the analysis populations, derivation of variables, convention of analysis scope, and statistical methodology for the analyses of safety and efficacy of pegunigalsidase-alfa (PRX-102) 2mg/kg administered every 4 weeks based on data collected per protocol PB-102-F50. Should the SAP and the protocol be inconsistent with respect to the planned analyses, the language of the SAP is governing. Any deviations from this SAP during the actual data analysis will be documented properly in a change request or a note-to-file document, as well as in the Clinical Study Report (CSR). The SAP will be finalized before the first database lock (DBL).

Analysis of PK endpoints will be presented in a separate document.

## 3. OBJECTIVES AND ENDPOINTS

### 3.1 Objectives

To evaluate the safety, efficacy, and PK of pegunigalsidase-alfa (PRX-102) in patients with Fabry disease currently treated with currently commercially available Enzyme Replacement Therapy (ERT) (agalsidase-alfa or agalsidase-beta).

### 3.2 Endpoints

#### 3.2.1 Safety Endpoints

- Treatment-emergent adverse events (TEAE)
- Infusion-related reactions (IRR)
- Infusion premedication
- Treatment-induced anti- pegunigalsidase-alfa antibodies
- Clinical laboratory tests
- Physical examinations
- Injection site reactions
- Electrocardiogram (ECG)
- Vital signs

### 3.2.2 Efficacy Endpoints (Exploratory)

- Estimated Glomerular Filtration Rate (eGFRCKD-EPI)
- eGFR slope
- Plasma Globotriaosylsphingosine (Lyso-Gb3)
- Plasma Globotriaosylceramide (Gb3)
- Urine Lyso-Gb3
- Urine Protein/Creatinine Ratio (UPCR) spot urine test
- Left Ventricular Mass Index (g/m^2) by echocardiogram
- Usage of pain medication
- Stress test
- Short form Brief Pain Inventory (BPI)
- Mainz Severity Score Index (MSSI)
- Quality of Life (QoL) EQ-5D-5L
- Fabry Clinical Events (FCE)

### 3.2.3 PK Endpoints

PK endpoints will include (but not restricted to) the following endpoints:

- Cmax
- Tmax
- T1/2
- AUC0-t
- AUC0-∞

## 4. STUDY DESIGN

This is an open-label switch over study of pegunigalsidase alfa (PRX-102) treatment in patients previously treated with ERT (agalsidase-alfa or agalsidase-beta), for at least 3 years and on a stable dose for at least the last 6 months.

Patient age will be 18 to 60 years, with a documented diagnosis of Fabry Disease (FD), and eGFRCKD-EPI at screening of 30 mL/min/1.73 m^2 or more and linear negative slope no worse than -2 mL/min/1.73 m^2/year based on at least 4 serum creatinine values over approximately 2 years (and including the value at screening).

Eligible patients will be enrolled and switched from their current ERT to receive intravenous (IV) infusions of pegunigalsidase-alfa 2 mg/kg every 4 weeks for 52 weeks. The protocol allows that in case of clinical deterioration, the dosing regimen may be changed to 1.0 mg/kg every two weeks at the Investigator's discretion. Patients will have the option to be enrolled to an open-label extension study upon completion of the study.

#### **4.1      Sample Size and Statistical Power Consideration**

Thirty patients participated in the study. This sample size was determined pragmatically and is adequate to evaluate the safety of switching from previous ERT every 4 weeks in this orphan disease in which patient recruitment is difficult. The sample size is not based on statistical considerations.

## 4.2 Study Diagram and Flow Chart

**Table 1: Study Assessments**

Calendar (week)		Day1	2	4	8	12	16	20	24	28	32	36	40	44	48	52
Activity /Visit Number/ Inf	S	V1	2week s	V2	V3	V4	V5	V6	V7	V8	V9	V10	V11	V12	V13	V14
Sign IC	X															
Assign screening number	X															
Inclusion/exclusion criteria	X	X														
Demographics	X															
Medical & Specific FD history including major clinical events	X															
Physical examination	X	X				X			X				X			X
Body weight	X	X							X							X
Body height	X															
Vital signs 	X	X		X	X	X	X	X	X	X	X	X	X	X	X	X
Review of medications				X	X	X	X	X	X	X	X	X	X	X	X	X
Pain medications	X	X														
Pre-medication Use																
Alfa-galactosidase activity in plasma	X															
Alfa-galactosidase activity in leucocytes	X															
Urine protein/creatinine ratio (UPCR)	X	X				X			X				X			X
Hematology	X	X				X			X				X			X
PT and PTT	X															
Biochemistry	X	X				X			X				X			X
Serum creatinine and Cystatin C	X	X		X	X	X	X	X	X	X	X	X	X	X	X	X
Vitamin D	X															
Serum pregnancy ( $\beta$ HCG) for females	X															
Urine pregnancy test for females		X				X			X				X			X
Urinalysis - dipstick	X	X				X			X				X			X
HBsAg, HCV & HIV	X															
Short Form Brief Pain Inventory (BPI)		X							X							X
Anti-Drug Antibodies (IgG) 	X	X	X	X		X			X				X			X
Plasma PK 			X						X				X			X
Electrocardiography (ECG)	X	X				X			X				X			X
Chest X-ray 	X									X						
Quality of Life (5Q-5D-5L)			X													X
Mainz Severity Score Index (MSSI)			X													X
Request patient approval by Medical			X													

Calendar (week)		Day1	2	4	8	12	16	20	24	28	32	36	40	44	48	52
Activity /Visit Number/ Inf	S	V1	2week s	V2	V3	V4	V5	V6	V7	V8	V9	V10	V11	V12	V13	V14
Monitor																
Medical Monitor approval			x													
Echocardiography			x							x						x
Cardiac function assessment (stress test)			x													x
Brain MRI			x													x
Adverse events assessments		x		x	x	x	x	x	x	x	x	x	x	x	x	x
Mutation analysis		x														
Con Meds	x	x		x	x	x	x	x	x	x	x	x	x	x	x	x
Urine lyso Gb3 concentration		x				x			x				x			x
Plasma Gb3 concentration 		x				x			x				x			x
Plasma Lyso Gb3 concentration 		x				x			x				x			x
Study Drug IV infusion 		x		x	x	x	x	x	x	x	x	x	x	x	x	x
Observe Patient 		x		x	x	x	x	x	x	x	x	x	x	x	x	x
Call Patient 		x														

 Will be performed only for patients who have not had the test during the last 3 months before screening

 Will be performed pre-infusion

 PK Time points: pre-infusion (baseline); 1 hour after the beginning of the infusion; at the end of the infusion, at  $1\pm0.25$ ,  $2\pm0.25$ ,  $4\pm0.25$ ,  $8\pm0.25$ ,  $24\pm0.5$ ,  $48\pm3$ , and  $96\pm3$  hours post-infusion and at  $14\pm3$ ,  $21\pm3$  and  $28\pm3$  days post-infusion

Patients who signed inform consent to this version (Version 4) before reaching Visit 7 (week 24), will perform PK at Visit 7; patients who signed inform consent after Visit 7 will perform PK at visit 11 (week 40).

 Evaluate vital signs: blood pressure, pulse, temperature and respiration rate; any time pre-infusion, every 30 ( $\pm10$ ) minutes during the first hour of the infusion, and from the second hour, 60 ( $\pm10$ ) minutes up to the end of the clinical observation, and at the end of the observation time, if the patient tolerates the infusion. Otherwise, evaluate vital signs every 15 minutes until achieving tolerability.

 According to [Appendix 8](#)

 24 hours post dosing first infusion

 Evaluate the injection site

 In patients who tolerate the infusions well, the infusion rate can be adjusted according to [Appendix 8](#).

## 5. ANALYSIS POPULATIONS (ANALYSIS SETS)

### 5.1 Safety Population

The safety population consists of all subjects who received at least one dose (partial or complete) of pegunigalsidase alfa in the study. All safety analyses will be based on this population.

### 5.2 Efficacy Population

The efficacy population consists of all subjects who received any dose of pegunigalsidase alfa 2 mg/kg in the study and who have at least one post-baseline visit with an efficacy evaluation. All efficacy analyses will be based on this population.

## 6. TREATMENT DESCRIPTIONS

Unless otherwise indicated, on the summary tables, the treatment will be identified as PRX-102, where applicable.

## 7.2 Missing Data

Imputations of missing data associated with AE severity and relatedness are specified in Section 10.2. Below are imputations rules related to missing or incomplete dates of AE or medication. No other imputations will be made for missing safety or efficacy endpoints.

### 7.2.1 Partial or Missing Dates of Medication

The following imputations will be used in case of incomplete dates for medications :

- The middle of the month (i.e. 15th) will be used if only the day is missing
- In case the year is not missing, but the month is missing, the month will be imputed to July. If the day is missing as well then it will be imputed to the 1st of July
- No imputation will be done in case the year is missing.

In some of the analyses, a flag of whether a medication was used at a certain visit is needed (e.g. use of Angiotensin-Converting Enzyme Inhibitor (ACEi) or Angiotensin Receptor Blocker (ARB) treatment at baseline or usage of pain medication at baseline or in the last visit). In case partial start date and/or end date exist, imputation will be based on the above rule and determination of the flag will be based on the imputed dates. In case that the start date is missing the year, the determination of usage of a medication at different visits will be based on the stop date of the medication. If the year of the stop date is missing, then the determination will be based on the “Ongoing” status of the medication form as follows: if the ongoing status is Yes then it is assumed that the medication was taken throughout the study (including at baseline and last visits), and if the ongoing status is No then it is assumed the medication was stopped prior to the baseline visit.

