### **7.2.2 Partial or Missing Dates of Episodes of Acute Kidney Injury**

Episodes of Acute Kidney Injury (AKI) are reported by the investigators as AE. An AKI episode is defined between the start and the end date of the AKI AE. The following rules will be followed in case on incomplete start or end date of an AKI event:

- AKI start date:
  - If month and year are available and day is missing, the 1st of the month will be imputed. In case the event is during the month of the first infusion, it will be imputed to the date of 1st infusion.
  - If month is missing and year is available then if the year is the same as the year of 1st infusion then the date should be the date of 1st infusion. Otherwise the date should be set to January 1st.
  - If year is missing then the date should be imputed to date of 1st infusion.

- AKI end date:
  - If month and year are available and day is missing, the last day of the month will be imputed. In case the event is during the month of the last infusion, it will be imputed to the date of end of study.
  - If month is missing and year is available then if the year is the same as the year of last infusion then the date should be the last day in the study. Otherwise the date should be set to December 31st.
  - If year is missing then the date should be imputed to last day in the study.

Serum creatinine during episodes of acute kidney injury (AKI) will be excluded from the eGFR slope calculation and summary tables and considered to be missing.

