## **10.8 Prior and Concomitant Medication**

Prior and concomitant medications reported during the study will be coded by World Health Organization (WHO) Drug Dictionary Version 20160601E. Prior and concomitant medication will be tabulated overall by count and percentage with each medication by standardized medication name within medication class. Medication class will be listed alphabetically.

Listing of medication will include start and end date and whether the drug was taken prior to 1st infusion of pegunigalsidase alfa. If the date is incomplete, the following rules will be used to flag that the drug was taken prior to 1st infusion:

- If the month and/or day are missing, and the year is earlier than year the 1st infusion
- If the day of the month is missing, the year is the same year as 1st infusion and the month is earlier than the month of 1st infusion.

In all other cases, it will be assumed that the drug was taken after the 1st infusion.

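### SAP 7.2.1 can impute a medication stop before its known start, and the 10.8 prior-use marker in the listing can contradict the 7.2.1 flags used in the tables

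*SAP*

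**What the plan says.** SAP 7.2.1 covers incomplete medication dates. The 15th "will be used if only the day is missing". If the month is missing too, "the month will be imputed to July", on the 1st. Start and stop dates are not distinguished. For use at a given visit, "determination of the flag will be based on the imputed dates". When the start year is missing the stop date decides. When the stop year is missing as well, the Ongoing field decides: "if the ongoing status is Yes then it is assumed that the medication was taken throughout the study (including at baseline and last visits"; otherwise, "if the ongoing status is No then it is assumed the medication was stopped prior to the baseline visit".

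SAP 10.8 has its own rule for a marker in the medication listing: "Listing of medication will include start and end date and whether the drug was taken prior to" the first infusion. An incomplete date counts as prior only if its year is earlier than that of the first infusion, or the year is the same and the known month is earlier. Then: "In all other cases, it will be assumed that the drug was taken after the" first infusion. Section 10.8 does not say whether the date meant is the start or the end date, and neither section refers to the other's rule.

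SAP 7.2.2 treats start and end separately for acute kidney injury. For an end date, for example: "If year is missing then the date should be imputed to last day in the study".

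**The concern.** There are two separate problems.

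The first lies inside 7.2.1. The same midpoint serves as start and as stop, and nothing requires the stop to follow the start. The rule can therefore produce an impossible interval, which registers no use at any visit. The flags taken from these dates define the ACEi/ARB-at-baseline subgroup (SAP 7.5) and both ends of the pain-medication shift table (SAP 9.8). The subgroup enters the baseline tables, the eGFR slope with a 95% CI for the difference (9.2), the UPCR categories and shift (9.6) and exposure (10.1). Under 7.5, anyone not identified as an ACEi/ARB user becomes a non-user, so a missed user is not visible as missing. A group below 5 may also be skipped.

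The second lies between 7.2.1 and 10.8. Baseline is Visit 1 before the first infusion (SAP 7.3), so in use at baseline and taken before the first infusion refer to almost the same moment. Two rules for it mean that the listing can contradict the tables it is meant to support.

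**Working it through.** The plan has no figure to reproduce here. The check applies both rules literally to a 365-day year; 2018 is used only for illustration. For 10.8, *the date* is read as the start date, which is an assumption.

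**A. Stop imputed before a known start (7.2.1 alone)**

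- Year-only stop, known start in the same year: the stop becomes 1 July and precedes every start from 2 July on. That is 30 + 31 + 30 + 31 + 30 + 31 = 183 of 365 start dates.
- Day-missing stop, known start in the same month: the stop becomes the 15th and precedes every start from the 16th on. That is 7 × 16 + 4 × 15 + 13 = 185 of 365 start dates.
- The same gap works in reverse: a year-only start can be set after a known stop earlier in that year.

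*Example.* Known start 10 July 2018, stop recorded only as 2018, first infusion 20 October 2018. The stop becomes 1 July, 9 days before the start, and the baseline flag is No. The stop could lie anywhere from 10 July to 31 December: 22 + 31 + 30 + 31 + 30 + 31 = 175 dates. Those from 20 October on, 12 + 30 + 31 = 73, mean use at baseline. So 73/175 = 42% of the possible stop dates contradict the flag.

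A start of 10 October with a year-only stop that year is likewise given a stop of 1 July. There the baseline flag can be wrong only if Visit 1 falls between 10 October and 31 December. An impossible interval is thus not always a wrong flag: the visit must also lie within the true period of use.

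**B. 7.2.1 against 10.8**

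| Record | 7.2.1 | 10.8 | When they conflict |
|---|---|---|---|
| Start and stop years missing, Ongoing = Yes | in use at baseline | after first infusion | always |
| Start known only as the year of first infusion | starts 1 July | after first infusion | infusion from 2 July on (183 of 365 dates) |
| Start in the month of first infusion, day missing | starts on the 15th | after first infusion | infusion from the 16th on (185 of 365 dates) |

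The mirror of the first row also conflicts: with both years missing and Ongoing = No, 7.2.1 places all use before baseline and 10.8 places it after.

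For all other incomplete starts with a known year, the rules were compared over 365 infusion dates and the previous, same and following year. The number of combinations is 365 × (13 + 11 + 13) = 13,505, with 0 conflicts. The disagreement is confined to the patterns above.

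**C. Weight of one flag**

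SAP 4.1 gives 30 patients: 1/30 = 3.3% move between levels per changed flag. A wrong record changes a patient's ACEi/ARB flag only if no other record shows use at that visit.

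**The case against.** A reader might infer that the clash between the two sections makes the table flags wrong. The documents do not support this. The flags follow 7.2.1 alone, and the 10.8 rule feeds only a listing marker. For an ongoing drug of unknown start, 7.2.1 already gives the sensible answer, use at baseline; only the listing differs.

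A reader might also take the shares near one half as error rates. They are shares of calendar dates within selected patterns, and the documents give no frequency of incomplete dates.

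The design limits the problem. Medications are reviewed at screening, at Visit 1 and at each infusion visit (Protocol 9.1 and 9.2). An ACEi/ARB started or changed in the 4 weeks before screening is an exclusion (6.3.2), and starting one on study needs sponsor approval (7.9). The eCRF has edit checks and queries, and missing data must be explained (11.2). This makes the problem records less likely, above all for ACEi/ARB, but does not make the stated rule safe when one occurs.

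Midpoint imputation is itself a permissible choice. Copying the earliest-start, latest-end logic of 7.2.2 is tempting, but that rule serves to exclude creatinine values during a kidney episode. Applied to medications, it would set a year-only on-study start to 1 January and could carry a drug that ended long ago through baseline.

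Finally, no tests are planned (SAP 7.4) and efficacy is exploratory. All of this limits the size of the problem but leaves both gaps in the text.

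**Conclusion.** The point holds in two limited parts. First, 7.2.1 as written produces impossible intervals for two identifiable patterns of incomplete stop date, and the resulting flag is wrong when the baseline or last visit falls within the true interval of use. Second, the 10.8 marker contradicts the 7.2.1 flags for the patterns in the table, so the listing disagrees with the tables without changing them.

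The number of affected patients is unknown and could be anywhere from 0 to 30. The consequences stay within descriptive output: the ACEi/ARB subgroup and the pain-medication shift table.

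The conclusion assumes that 10.8 refers to the start date and that the rules are programmed literally. The text that, by the table of contents, should be SAP 7.1 is not in the copy reviewed, so a general date check there cannot be excluded.

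**What to change.** 1. Keep the midpoint rule in 7.2.1, and add that an imputed stop may not be earlier than the known start, that an imputed start may not be later than the known stop, and that both must agree with the Ongoing status.
2. In 10.8, derive the prior-use marker from the same imputed dates and Ongoing rule as 7.2.1, and state that it refers to the start date.

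Step 1 removes stop-before-start intervals by construction, and step 2 removes the conflict between listing and tables. The cost is a few lines of SAP text and one shared derivation.

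A bounded date is still a guess within the possible range. In the example above, the stop would move from 1 July to 10 July and the baseline flag would remain No. Records whose flag depends on an imputed date are therefore worth querying before database lock.

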### **7.2.2 Partial or Missing Dates of Episodes of Acute Kidney Injury**

Episodes of Acute Kidney Injury (AKI) are reported by the investigators as AE. An AKI episode is defined between the start and the end date of the AKI AE. The following rules will be followed in case on incomplete start or end date of an AKI event:

- AKI start date:
  - If month and year are available and day is missing, the 1st of the month will be imputed. In case the event is during the month of the first infusion, it will be imputed to the date of 1st infusion.
  - If month is missing and year is available then if the year is the same as the year of 1st infusion then the date should be the date of 1st infusion. Otherwise the date should be set to January 1st.
  - If year is missing then the date should be imputed to date of 1st infusion.

- AKI end date:
  - If month and year are available and day is missing, the last day of the month will be imputed. In case the event is during the month of the last infusion, it will be imputed to the date of end of study.
  - If month is missing and year is available then if the year is the same as the year of last infusion then the date should be the last day in the study. Otherwise the date should be set to December 31st.
  - If year is missing then the date should be imputed to last day in the study.

Serum creatinine during episodes of acute kidney injury (AKI) will be excluded from the eGFR slope calculation and summary tables and considered to be missing.

